3 LIST OF ABBREVIATIONS AND DEFINITION OF TERMS

| Abbreviation | Explanation |
|-----------------------|--|
| ADaM | Analysis Data Model |
| AE | Adverse event |
| A _e | Amount excreted in urine |
| ATC | Anatomical therapeutic chemical |
| AUC | Area under the plasma concentration vs. time curve |
| AUC _{0-inf} | AUC from 0 to infinity |
| AUC _{0-last} | AUC from 0 to time of last measurable plasma concentration |
| b.i.d. | Two times a day (bis in die) |
| BLQ | Below lower limit of quantification |
| BMI | Body mass index |
| C _{avg} | Average concentration over dosing interval |
| CDISC | Clinical Data Interchange Standards Consortium |
| CI | Confidence interval |
| CL/F | Apparent total body clearance following extravascular administration |
| C _{max} | Maximum observed concentration |
| C _{min} | Minimum observed concentration at the end of the dosing interval |
| | |
| CTP | Clinical trial protocol |
| CV | Coefficient of variation |
| DDP | Data display plan |
| ECG | Electrocardiogram |
| eCRF | Electronic case report form |
| FAS | Full analysis set |
| FDA | United States Food and Drug Administration |
| F _e | Fraction of dose excreted in urine |
| FIH | First-in-human |
| Geo | Geometric |
| IG | Implementation guideline |
| IMP | Investigational medicinal product |
| lambda _z | Terminal elimination rate constant |

| Abbreviation | Explanation |
|-------------------|--|
| lin | Linear |
| LLOQ | Lower limit of quantification |
| log | logarithmic |
| LS | Least square |
| MAD | Multiple-ascending dose |
| Max | Maximum |
| MedDRA | Medical dictionary for regulatory activities |
| Min | Minimum |
| NA | Not applicable/not available |
| NC | Not calculated |
| NCA | Non-compartmental analysis |
| PK | Pharmacokinetic(s) |
| PKAS | PK analysis set |
| PT | Preferred term |
| SAD | Single-ascending dose |
| SAE | Serious adverse event |
| SAP | Statistical analysis plan |
| SAS | Statistical analysis system |
| SD | Standard deviation |
| SDTM | Trial data tabulation model |
| SOC | System organ class |
| T _{last} | Time of occurrence of last observed plasma concentration |
| T _{max} | Time of occurrence of C _{max} |
| T _{1/2} | Terminal elimination half-life |
| ULOQ | Upper limit of quantification |
| V _z /F | Volume of distribution (associated with terminal phase) following extravascular administration |
| WHO | World Health Organization |

4 INTRODUCTION

This SAP gives a detailed description of the planned statistical analysis for trial IRL757C001.

4.1 Trial design

This is a prospective, single-centre, randomised, double-blind, placebo-controlled, phase I, First-In-Human (FIH) trial evaluating the safety and tolerability of single and multiple ascending oral doses of IRL757 in healthy volunteers.

Single Ascending Dose (SAD) part: A randomised, double-blind, placebo-controlled single ascending dose trial in healthy volunteers.

Multiple Ascending Dose (MAD) part: A randomised, double-blind, placebo-controlled multiple dosing trial in healthy volunteers.

Please see the clinical trial protocol (CTP) for additional details.

4.2 Trial objectives and endpoints

Table 1 Trial objectives and endpoints

| Objectives | Endpoints | Assessments | Analyses | Data display plan (DDP) |
|--|--|--|---|--|
| Primary objective | Primary endpoints | | | |
| To evaluate the safety and tolerability of IRL757 after single and repeated dosing in healthy volunteers. | Frequency, seriousness and intensity of adverse events (AEs). | AE reporting and questioning | Descriptive statistics, Section 9.1.1 | SAD: Section 10.2.2.1 MAD: Section 11.2.2.1 |
| | Physical examination | Physical examinations | Descriptive statistics, Section 9.1.2 | SAD: Section 10.2.2.2 MAD: Section 11.2.2.2 |
| | Columbia-Suicide Severity Rating Scale (C-SSRS) | C-SSRS questionnaire | Listings, Section 9.1.3 | SAD: Listing MAD: Listing |
| | Electrocardiogram (ECG) | 12-lead safety ECG | Descriptive statistics, Section 9.1.4 | SAD: Section 10.2.2.3 MAD: Section 11.2.2.3 |
| | Telemetry recordings (SAD part of the trial only) | Telemetry | Descriptive statistics, Section 9.1.5 | SAD: Section 10.2.2.4 MAD: NA |
| | Vital signs | Blood pressure and pulse | Descriptive statistics, Section 9.1.6 | SAD: Section 10.2.2.5 MAD: Section 11.2.2.4 |
| | Safety laboratory measurements | Blood sampling for haematology, clinical chemistry and coagulation | Descriptive statistics, Section 9.1.7 | SAD: Section 10.2.2.6 MAD: Section 11.2.2.5 |
| Secondary objectives | Secondary endpoints | | | |
| 
 To determine the single and multiple dose PK characteristics of IRL757 and its 3 main metabolites in healthy volunteers. To evaluate the interaction with food after single oral dosing of IRL757 on its PK characteristics and its 3 main metabolites in healthy volunteers. | 
 SAD part: Area under the plasma concentration-time curve $AUC_{0-\infty}$, AUC_t, AUC_{0-24h}, maximum concentration (C_{max}), time to maximum concentration (T_{max}), terminal elimination rate constant (λ_{dz}), terminal half-life ($T_{1/2}$), total apparent clearance of drug from plasma (CL/F), volume of distribution (V_z/F), amount excreted in urine (A_e), fraction of the dose excreted in urine (F_e) (for IRL757), renal clearance CL_R. Amount excreted in urine (A_e) for the metabolites. Relative bioavailability after fed and fasting conditions determined from AUC_t and $AUC_{0-\infty}$, and C_{max}. | PK plasma and urine sampling | Descriptive statistics and dose proportionality analysis, Section 9.2.1 | SAD: Sections 10.2.3.1, 10.3.1.1 and 10.3.1.2 MAD: Sections 11.2.3.1, 11.3.1.1 and 11.3.1.2 |

| Objectives | Endpoints | Assessments | Analyses | Data display plan (DDP) |
|---|---|----------------------------------|---|-------------------------|
| | 
 • MAD part, Day 1: $AUC_{0-\tau}$, C_{max}, T_{max}, λ_{dz}, $T_{1/2}$, Day 10: $AUC_{0-\tau}$, C_{max}, T_{max}, λ_{dz}, $T_{1/2}$, CL/F, V_z/F, fraction of the dose excreted in urine (F_e) (for IRL757) for the last dose interval in the morning of Day 10, renal clearance CL_R. Amount excreted in urine (A_e) for the metabolites. • Dose proportionality after single dose based on $AUC_{0-\infty}$ and C_{max}. • Dose proportionality after multiple doses based on $AUC_{0-\tau}$ and C_{max}. • Accumulation ratio (AR) after multiple doses based on C_{max} ratio and ratio $AUC_{0-\tau}$ (Day 10) to $AUC_{0-\tau}$ for the first dose interval on Day 1. | | | |
| Exploratory objectives | Exploratory endpoints | | | |
| To characterize the metabolite profile in human plasma and urine and compare metabolite exposures between human and the safety species rat and dog. | 
Metabolite In Safety Testing (MIST) analysis of the metabolite profile in plasma in comparison with the metabolite profile in plasma from non-clinical safety studies.
 
Profile of excreted metabolites in the urine.
 | Blood sampling for MIST analysis | The analyses and results pertaining to the exploratory endpoints, MIST analysis and urine metabolite profile, will be detailed in a separate report, and hence are not covered in this SAP. | |

4.3 Randomisation and number of subjects

In both the SAD and MAD part of the trial, subjects in each cohort will be randomised to treatment with either IRL757 or placebo (3:1). Sentinel-dosing will be applied.

Forty (40) healthy subjects will be included in the SAD part of the trial.

Six (6) additional healthy subjects will be included in the food interaction sub-study.

The MAD part of the trial will include 24 or 36 healthy subjects, depending on the number of dose levels assessed, and defined following review of the data of the SAD part of the trial (two (2) or three (3) dose levels).

In the MAD part, up to twelve (12) additional subjects may also be included if recommended by the internal safety review committee.

4.4 Subject replacement

The trial subjects withdrawn for medical/safety reasons will not be replaced.

Voluntary withdrawals can be replaced if they are not evaluable. See CTP for additional details.

4.5 Blinding

This is a double-blinded trial, and the allocation of treatments will not be disclosed until clean file has been declared and the database has been locked.

5 STATISTICAL AND ANALYTICAL PLANS

5.1 Statistical hypotheses

The primary objective of this trial is to assess safety and tolerability, and no hypothesis testing will be conducted on data related to these endpoints. Additionally, as part of the secondary objectives and endpoints, this trial aims to test the hypothesis that pharmacokinetic AUC and C_{\max} are proportional to the dose administered. Please refer to sections 9.2.1.1-9.2.1.2 below for more details about the dose proportionality analyses.

5.2 Sample size calculation

No formal sample size calculation has been performed for this trial. The size of the cohorts/dose groups is considered sufficient to provide adequate information on the safety and PK parameters for the purpose of this trial.

5.3 Definition of analysis sets

The analysis sets defined for the trial are outlined in Table 2.

Table 2 Analysis sets

| Analysis set | Definition | Comment | Use of analysis set |
|-------------------------------------|---|--|---|
| Full analysis set (FAS) | All subjects who have received treatment with IMP and have available data. | | The FAS will be used for safety and tolerability assessments and description of trial population. |
| Pharmacokinetic analysis set (PKAS) | All subjects who received treatment with IMP, who provided an evaluable plasma concentration profile and who have no AEs or protocol deviations judged to affect the PK analysis. Individual PK values may be excluded from the analysis. | This set is referred to as the Per Protocol Analysis Set (PPAS) in the CTP. In the CTP, there is slightly different wording, but the definitions encompass the same subjects. Additionally, the SAP specifies that there should be no AEs that could affect the PK analysis for the included subjects. | PK endpoints. |

5.4 Definition of baseline

Baseline is defined as the latest measurement prior to (first) IMP exposure in each treatment period.

5.5 Rounding principles

Generally, no rounding of data will be done prior to calculating statistics. However, if reported data contains more than 8 significant digits it will be rounded to 8 significant digits in the database.

In statistical output and descriptive summaries, the following principles will be used:

- Data will be presented as reported in input data in listings.

- Two (2) significant digits will be used for percentages (for example relative change from baseline).
- p-values and similar statistical output will be presented using 4 decimal places.
- Three (3) significant digits will be used for PK parameters when presenting min and max values in tables.
- Descriptive summaries (e.g., mean, SD, median etc.) of PK parameters will be presented with 4 significant digits.
- Descriptive summaries (e.g., mean, SD, median etc.) of all other numerical data will be presented with one extra decimal compared to reported input data.

5.6 Significance level

All statistical hypotheses in this trial will be answered using two-sided 90% confidence intervals.

5.7 Handling of dropouts, missing data and outliers

Outliers will be included in summary tables and listings and will not be handled separately in any analyses. All collected data, even if not tabulated, will be listed. Generally, no imputation of data will be performed. However, when calculating statistics for PK plasma concentrations, concentrations under LLOQ will be replaced with LLOQ/2 if more than 50% of the values for a given time point are above LLOQ. For figures presenting individual PK concentrations, no imputation is performed for values under LLOQ. For imputation of PK plasma concentration below LLOQ with the purpose of calculating PK parameters, see Section 9.2.1.

Safety laboratory concentrations under LLOQ will be replaced with LLOQ/2 and concentrations over ULOQ will be replaced with ULOQ for the purpose of calculating descriptive statistics.

In case of missing start and stop times of AEs that cannot be investigated further, missing data will be imputed according to a worst-case scenario, i.e., start time will be imputed as the closest time point post first intake of IMP and end time as 23:59, resulting in the longest possible treatment emergent duration of the AE.

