There will be an interval of at least one (1) week between last administration in a cohort and initiation of next cohort to allow time for PK and safety data to be analysed, evaluated and reviewed by the iSRC. The iSRC will have the choice to recommend to escalate the dose as planned, reduce or increase the dose escalation step, repeat the dose, reduce the dose or terminate the trial.

The decision on dose levels will be done following the SAD part of the trial and a cautious selection of dose will be done if dosing is expected to approach the exposure limit.

Screening (Visit 1) will take place between Day -28 and Day -1.

Eligible subjects will be confined to the research clinic from the evening before first dosing (Day -1) until Day 11 and will come back to the clinic on Day 12 for extended PK and safety samples (including 48 hours post the last morning dose). The subjects should be fasting overnight (10 hours) before dose administration on Day 1 and Day 10. A Follow-up Visit will be performed 5-10 days after last administration of IMP.

An additional third cohort (IRL757 Dose Level 3), with twelve (12) additional subjects may be implemented following the review of data of the SAD part of the trial. The cohorts are described in Table 2.

Table 2 MAD dosing groups

Cohort	Dose	Groups	
Cohort 1 (n=12)	Dose Level 1	2 + 3 + 3 + 4	Sentinel group (n=2): 1 active, 1 placebo Subsequent groups (n=3+3+4): 8 active, 2 placebo
Cohort 2 (n=12)	Dose Level 2	2 + 3 + 3 + 4	
Cohort 3 (n=12)	Dose Level 3	2 + 3 + 3 + 4	

Investigational Medicinal Products (IMP), dosage and mode of administration

IRL757 half-life is expected to be 2-7 hours.

IRL757 capsules [REDACTED]

Placebo capsules: [REDACTED]

Duration of treatment

Subjects included in the SAD part will be treated with one (1) single oral dose of IRL757 or placebo (see Table 1).

Subjects included in the food interaction sub-study will be treated with two (2) oral doses of IRL757.

Subjects included in the MAD part will receive two (2) daily oral doses of IRL757 or placebo for ten (10) consecutive days. The number of daily doses in the MAD part of the trial will be confirmed following review of PK data from the SAD part of the trial.

Duration of each subject's involvement in the trial

Subjects will be screened for eligibility according to trial-specific inclusion/exclusion criteria at Visit 1 (Screening visit) within four (4) weeks prior to start of IMP administration.

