AE reporting			X	X	X	X	X	X	X	X
Concomitant medications	X	X	X	X	X	X	X	X	X	X
Admission to clinic		X				X				

¹ Visit 3 is performed after a minimum of 5 half-lives of the IMP and no later than 14 days after the first IMP administration.

² Pre-dose.

³ Symptom-driven physical examination.

⁴ Pre-dose and 30 min, 1, 2, 4, 8, 12 and 24 hours post-dose.

⁵ Within 60 min pre-dose and 20 (±2) min, 40 (±4) min, 1 hour (±6 min), 2 hours (±12 min), 3 hours (±18 min), 4 hours (±24 min), 6 hours (±30 min), 8 hours (±30 min), 10 hours (±30 min), and 12 hours (±30 min) post-dose.

⁶ 24 hours (±1 hour) post-dose.

⁷ 48 hours (±1 hour) post-dose.

⁸ Standardized breakfast meal is provided to the subject within 30 min prior to IMP administration.

⁹ The dose used for the food interaction sub-study will be determined after completion of Cohort 4 (Dose Level 4) in the SAD part of the trial.

¹⁰ Serum at screening, urine at Day -1 and Follow-up.

¹¹ Triplicate ECGs separated by at least 1 min.

Table 6 Detailed schedule of events, SAD part of the trial, food interaction sub-study, in-clinic Day -1 to Day 3

	In-clinic															
Visit No.	Visit 2 (fasted condition)/Visit 3 (fed condition)															
Day	Day -1	Day 1													Day 2	Day 3
Time /assessment	Admission	Pre-dose	0	20min	30min	40min	1 h	2 h	3 h	4 h	6 h	8 h	10 h	12 h	24 h	48 h
Inclusion/exclusion criteria		X														
Physical examination		X ⁸														X ⁹
C-SSRS																X
Weight, BMI	X															
Blood pressure, heart rate, respiratory rate	X	X			X		X	X		X		X		X	X	X
Body temperature	X														X	X
Haematology, clinical chemistry, coagulation	X															X
Pregnancy test	X ⁷															
Drugs of abuse	X															
Alcohol screen	X															
ECG	X ¹	X ²					X	X	X		X			X	X	X
Standardized breakfast meal		X ³														
IMP administration			X													
PK blood sampling ⁴		X		X		X	X	X	X	X	X	X	X	X	X	X
Baseline symptoms	X ⁵	X ⁵														
AE reporting	X ⁶	X ⁶	X													
Concomitant medications	X	X	X													

¹ Triplicate ECGs separated by at least 1 min at Day -1.

² Within 60 min prior to dose at Pre-dose.

³ Meal to be started within 30 min prior to administration of IMP. Applicable only to Visit 3 (fed condition).

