9 STATISTICAL METHODOLOGY

In general, data will be presented in tables with the number of observations, arithmetic mean, standard deviation (SD), median, minimum and maximum value for continuous data. In addition, 95% confidence intervals (CIs) will be added for ECG, vital signs and safety laboratory data. Categorical data will be presented with counts and percentages. All collected data will be listed by subject and treatment, except for data pertaining to the exploratory endpoints, MIST analysis and urine metabolite profile, which will be reported elsewhere. Data is generally presented by part, treatment (active/placebo, or for the SAD sub-study, fasted/fed conditions), and dose group.

SAD and MAD data will be presented separately. Additionally, the tables and figures for the food interaction sub-study will be presented separated from those of the other SAD dose groups. The data for subjects receiving placebo will be presented pooled across groups, for SAD and MAD respectively.

Details on statistical analyses and descriptive summaries are specified below.

All statistical analyses and descriptive summaries will be performed using SAS version 9.4 (SAS institute, Cary, NC).

PK parameters will be calculated by Non-Compartmental Analysis (NCA) using the software Phoenix WinNonlin[®] version 8.3(Certara, U.S.A).

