9.1 Analysis of the primary endpoints

9.1.1 Adverse Events (AEs)

AEs and SAEs will be recorded from the time when informed consent is obtained until the Follow-up Visit. AEs that occur before first treatment with IMP (baseline symptoms) will be listed separately.

All AEs will be described in terms of the treatment at which they occurred. AEs will be summarised by System Organ Class (SOC) and Preferred Term (PT) using the Medical Dictionary for Regulatory Activities (MedDRA) vocabulary. The number of subjects reporting AEs, and the number of AEs reported will be presented. The events will be tabulated by SOC, PT and by severity and relationship to IMP. SAEs will be presented in the same tabulations.

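### The AE start-time imputation in SAP 5.7 has no per-period anchor, so in the food sub-study an untimed AE on the fed dosing day can be counted under fasted

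*SAP*

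**What the plan says.** SAP 5.7 covers AE start and stop times that are missing and cannot be investigated further. The "start time will be imputed as the closest time point post first intake of IMP" and the "end time as 23:59, resulting in the longest possible treatment emergent duration of the AE". The rule mentions neither treatment periods nor a second dose.

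The protocol synopsis, under duration of treatment, states: "Subjects included in the food interaction sub-study will be treated with two (2) oral doses of IRL757". Protocol Tables 5 and 6 fix the order, with fasted at Visit 2 and fed at Visit 3. Table 5, footnote 1 gives the gap: "Visit 3 is performed after a minimum of 5 half-lives of the IMP and no later than 14 days after the first IMP administration".

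SAP 9 presents data by treatment, "or for the SAD sub-study, fasted/fed conditions". SAP 9.1.1 adds: "All AEs will be described in terms of the treatment at which they occurred". It does not say whether that is decided by onset time, by visit or by study element.

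SAP 5.4 does use a period-specific anchor for baseline, namely the last value "prior to (first) IMP exposure in each treatment period".

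**The concern.** The rule has one anchor per subject, but the sub-study has two doses per subject and reports its results by dose condition. By the fed dosing day the first intake is already days in the past. The anchor therefore no longer restricts the imputed time, and the earliest moment of that date satisfies it. An event that probably followed the fed dose can then be recorded as starting before that dose.

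Adverse events are a primary endpoint, and the fasted/fed split is how the sub-study reports them. Where an error of this kind occurs, it always runs from fed to fasted. A rule intended as a worst case would then remove an event from the dose taken that day and attach it to a dose taken at least five half-lives earlier.

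**Working it through.** The plan has no figure of its own to reproduce. The check is date logic plus one proportion.

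**Inputs from the documents**
- Anchor: first intake, with no period qualifier (SAP 5.7).
- Two doses, fasted then fed (Protocol synopsis; Tables 5 and 6).
- Gap: at least five half-lives and at most 14 days. With the synopsis half-life of 2 to 7 h, the minimum is 5 × 2 = 10 h to 5 × 7 = 35 h. Confinement lasts at least 48 h after each dose, so the two doses fall on different dates.
- Six subjects (Protocol synopsis; SAP 4.3).

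**Assumptions not in the documents**
- Both doses are given at 07:00, 08:00, 10:00 or 12:00, with a gap of 3, 7 or 14 days (12 combinations).
- *After intake* means one minute later.
- An event is fed if its onset is at or after the fed dose, otherwise fasted.

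**Formulas** for an untimed event dated D, the fed dosing day:
- Literal rule: start = the later of 00:00 on D and (fasted dose + 1 min).
- Per-period rule: start = the later of 00:00 on D and (fed dose + 1 min).

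**Worked case**: fasted dose on 1 January at 08:00, fed dose on 8 January at 08:00.
- Literal: the later of 8 January 00:00 and 1 January 08:01 is 8 January 00:00, which is 8 h before the fed dose. Counted as fasted.
- Per period: the later of 8 January 00:00 and 8 January 08:01 is 8 January 08:01. Counted as fed.

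| Fed dose | Literal start | Lead over fed dose | Literal duration to 23:59 | Per-period start | Per-period duration to 23:59 |
|---|---|---|---|---|---|
| 07:00 | 00:00 | 7 h | 23 h 59 min | 07:01 | 16 h 58 min |
| 08:00 | 00:00 | 8 h | 23 h 59 min | 08:01 | 15 h 58 min |
| 10:00 | 00:00 | 10 h | 23 h 59 min | 10:01 | 13 h 58 min |
| 12:00 | 00:00 | 12 h | 23 h 59 min | 12:01 | 11 h 58 min |

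The rows are the same for all three gaps. The literal rule gives fasted in 12 of 12 combinations, and the per-period rule gives fed in 12 of 12. Placing the start straight after the fasted dose, and so overriding the recorded date, also gives fasted in 12 of 12.

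**Where the problem stops.** On the fasted dosing day the literal rule works: an 08:00 dose gives 08:01. On the day after the fed dose, 00:00 is already later than that dose, so the event is fed either way. Only the fed dosing date is affected.

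**Size.** One subject is 1/6 = 16.7% of a condition. The change in the number of subjects with an event in a given category depends on that subject's other events in the category:

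| Other event in same category | Fasted incidence | Fed incidence |
|---|---|---|
| None | +16.7 points | −16.7 points |
| Fasted only | 0 | −16.7 points |
| Fed only | +16.7 points | 0 |
| Both | 0 | 0 |

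**The case against.** The strongest reply is that the documents do not fix the result. It needs two things: that *first intake* means first in the whole trial, and that events are assigned by comparing onset with the time of the fed dose.

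On the first, SAP 5.4 already uses *first* within a treatment period, and 5.7 could be meant the same way, in which case the event is fed. That is fair as a guess at intent, but the qualifier stands in 5.4 and not in 5.7, and a programmer working from 5.7 has to supply it.

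On the second, SAP 7.2 says that study elements have transition rules. If the fed element begins at Visit 3 admission, or if events are assigned by visit, an event set to 00:00 on the fed day is still fed. The sub-study design figure and the SAD adverse event table layouts, where this might be settled, are not shown in the public copy. Their absence there cannot be held against the plan. Against this, Protocol Table 6 (footnote 6) collects AEs at admission and before dosing specifically at the fed visit. Events can therefore arise at that visit before the fed dose, and onset time is the natural way to separate them.

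The literal rule also meets its stated aim of the longest duration: 23 h 59 min, against about 12 to 17 h under a per-period anchor. That is true, but duration is not what separates fasted from fed.

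Finally, the reach is small. The rule applies only to irrecoverable times, in six subjects under observation in clinic. No hypothesis is tested on safety, and SAP 5.5 has listings show data as reported, so a missing time should be visible. All of this stands, and it limits the importance of the point without removing it.

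**Conclusion.** The point holds as a conditional and minor one. SAP 5.7 states a rule that, read literally and combined with attribution by onset, can place an untimed fed-day event under fasted. The shift is at most 17 percentage points per condition for each affected subject, reached in both conditions only when that subject has no other event of the category in either. It rests on all six subjects being in the denominator and on a start time that cannot be recovered.

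A reader might infer that the plan definitely assigns such events to fasted. The documents do not support that, because the attribution method is not visible and a per-period reading of 5.7 is possible. Nor should a reader infer that the overall safety picture is distorted. Both sub-study conditions are IRL757, so only the split between them can change. Sub-study tables are presented separately from the other SAD groups, and the fasted/fed question does not arise for subjects in the single-dose SAD cohorts or the MAD part.

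**What to change.** In SAP 5.7, replace the anchor with: *first intake of IMP in the treatment period to which the AE start date belongs*. For this rule, let the fed period begin on the calendar date of the fed dose, so that an untimed event on either sub-study dosing day starts just after that day's dose and an event dated the day before is not pulled forward. In SAP 9.1.1, add one sentence: sub-study AEs are assigned to fasted or fed by onset, imputed where necessary, relative to the fed dose.

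Do not anchor to the most recent intake. MAD dosing is twice daily (Protocol Table 7, footnote 8; Table 8 shows Day 1 doses at 0 and 12 h). That wording would move an untimed Day 1 event to the evening dose, 12 h later, and shorten the duration the rule is meant to maximise. With the per-period wording, single-dose SAD and MAD are unchanged, because each of those subjects has one treatment period.

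The cost is a few words and a line of code. The downside is negligible: an untimed event that truly began earlier on the fed day, before the dose, would be counted as fed, which agrees with the worst-case intent.
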